**Cycle 1, Study Day 1 (and Study Day 8 for Dose Cohort 1 only)**

- 1) Verify eligibility criteria (Study Day 1 only, for all dose cohorts and dose-expansion phase)
- 2) Update screening history and physical examination findings (any new findings since screening; Study Day 1, only, for all dose cohorts and dose-expansion phase)
- 3) Assess for SAEs and protocol-related AEs
- 4) Update concomitant medications
- 5) Obtain body weight for dosing calculations (Study Day 1, only, for all dose cohorts and dose-expansion phase)
- 6) Blood collection prior to infusion of MEDI-575
  - Chemistry panel (AST/ALT, total bilirubin, creatinine, alkaline phosphatase, sodium, potassium, chloride, phosphorus, calcium, glucose, magnesium, albumin, and LDH)
  - Hematology (CBC, differential, and platelet count)
  - Serum concentration of MEDI-575
  - Circulating plasma biomarker analysis
  - Anti-MEDI-575 antibodies (Study Day 1, only, for all dose cohorts and dose-expansion phase)
- 7) Routine urinalysis
- 8) Urine  $\beta$ hCG (Study Day 1, only, for all dose cohorts and dose-expansion phase)
- 9) Karnofsky performance status (Study Day 1, only, for all dose cohorts and dose-expansion phase)
- 10) Focused physical examination (Study Day 1, only, for all dose cohorts and dose-expansion phase)

- 11) 12-lead ECG (prior to infusion), at the time of completion of infusion ( $\pm$  5 minutes), 2 hours ( $\pm$  15 minutes) post completion of infusion, and 6 hours ( $\pm$  15 minutes) post completion of infusion. All ECGs performed will be obtained in triplicate (ie, 3 ECGs should be obtained within approximately a 5-minute time interval). All ECGs should be done prior to PK draw for the corresponding time point.
- 12) Vital signs prior to infusion of MEDI-575 (temperature, blood pressure, pulse rate, respiratory rate)
- 13) Administration of MEDI-575
- 14) Monitor for AEs and SAEs
- 15) Monitor vital signs at 15, 30, and 45 minutes ( $\pm$  5 minutes) post initiation of infusion, at the completion of infusion ( $\pm$  5 minutes), and 30 and 60 minutes ( $\pm$  5 minutes) post completion of infusion
- 16) Blood collection immediately after and 2 and 6 hours ( $\pm$  15 minutes) post completion of infusion
  - Serum concentration of MEDI-575
  - Circulating plasma biomarker analysis

**Cycle 1, Study Day 2 (and Study Day 9 for Cohort 1, Only)**

- 1) Blood collection 24 hours ( $\pm$  2 hours) post completion of infusion
  - Serum concentration of MEDI-575
  - Circulating plasma biomarker analysis

**Cycle 1, Study Day 3 (and Study Day 10 for Cohort 1, Only)**

- 1) Vital signs
- 2) Assessment of AEs and SAEs
- 3) Update concomitant medications
- 4) Blood collection 48 hours ( $\pm$  2 hours) post completion of infusion
  - Chemistry panel (AST/ALT, total bilirubin, creatinine, alkaline phosphatase, sodium, potassium, chloride, phosphorus, calcium, glucose, magnesium, albumin, and LDH)
  - Hematology (CBC, differential, and platelet count)
  - Serum concentration of MEDI-575
  - Circulating plasma biomarker analysis

### **Cycle 1, Study Day 8 (and Study Day 15 for Cohort 1 only)**

- 1) Update concomitant medications
- 2) Blood collection (prior to infusion of MEDI-575 for weekly dosing schedule)
  - Chemistry panel (AST/ALT, total bilirubin, creatinine, alkaline phosphatase, sodium, potassium, chloride, phosphorus, calcium, glucose, magnesium, albumin, and LDH)
  - Hematology (CBC, differential, and platelet count)
  - Serum concentration of MEDI-575
  - Circulating plasma biomarker analysis
- 3) Routine urinalysis
- 4) Vital signs (prior to infusion of MEDI-575 for weekly dosing schedule) (temperature, blood pressure, pulse rate, respiratory rate)
- 5) Administration of MEDI-575 (**weekly dosing schedule**)
- 6) Assessment of AEs and SAEs
- 7) Monitor vital signs (at 15, 30, and 45 minutes [ $\pm$  5 minutes] post initiation of infusion, at the completion of infusion [ $\pm$  5 minutes], and 30 and 60 minutes [ $\pm$  5 minutes] post completion of infusion for weekly dosing schedule)
- 8) Blood collection (immediately after [ $\pm$  5 minutes] completion of infusion with MEDI-575 for weekly dosing schedule)
  - Serum concentration of MEDI-575
  - Circulating plasma biomarker analysis

### **Cycle 1, Study Day 15 (Cohorts 2 and Above) and 22 (Cohort 1 only)**

- 1) Update concomitant medications
- 2) Blood collection (prior to infusion of MEDI-575 for weekly dosing schedule)
  - Chemistry panel (AST/ALT, total bilirubin, creatinine, alkaline phosphatase, sodium, potassium, chloride, phosphorus, calcium, glucose, magnesium, albumin, and LDH)
  - Hematology (CBC, differential, and platelet count)
  - Serum concentration of MEDI-575
  - Circulating plasma biomarker analysis
- 3) Routine urinalysis
- 4) Vital signs (prior to infusion of MEDI-575 for weekly dosing schedule) (temperature, blood pressure, pulse rate, respiratory rate)

- 5) Administration of MEDI-575 (**weekly dosing schedule**)
- 6) Assessment of AEs and SAEs
- 7) Monitor vital signs (at 15, 30, and 45 minutes [ $\pm$  5 minutes] post initiation of infusion, at the completion of infusion [ $\pm$  5 minutes], and 30 and 60 minutes [ $\pm$  5 minutes] post completion of infusion for weekly dosing schedule)
- 8) Blood collection (immediately [ $\pm$  5 minutes] after completion of infusion with MEDI-575 for weekly dosing schedule)
  - Serum concentration of MEDI-575
  - Circulating plasma biomarker analysis

**Cycle 2 and All Subsequent Cycles, Study Day 1 (All Dose Cohorts and Dose Expansion Phase)**

- 1) Update concomitant medications
- 2) Obtain body weight for dosing calculations
- 3) Blood collection prior to infusion of MEDI-575
  - Chemistry panel (AST/ALT, total bilirubin, creatinine, alkaline phosphatase, sodium, potassium, chloride, phosphorus, calcium, glucose, magnesium, albumin, and LDH)
  - Hematology (CBC, differential, and platelet count)
  - Serum concentration of MEDI-575
  - Circulating plasma biomarker analysis
  - Serum tumor biomarkers analysis (as relevant to tumor type)
  - Circulating tumor cell analysis
  - RNA analysis
  - Anti-MEDI-575 antibodies
- 4) Routine urinalysis
- 5) Urine  $\beta$ hCG
- 6) Karnofsky performance status
- 7) Focused physical examination
- 8) 12-lead ECG prior to dosing, only. All ECGs performed will be obtained in triplicate (ie, 3 ECGs should be obtained within approximately a 5-minute time interval).
- 9) Vital signs prior to infusion of MEDI-575 (temperature, blood pressure, pulse rate, respiratory rate)
- 10) Administration of MEDI-575

- 11) Assessment of AEs and SAEs
- 12) Monitor vital signs at 15, 30, and 45 minutes ( $\pm$  5 minutes) post initiation of infusion, at the completion of infusion ( $\pm$  5 minutes), and 30 and 60 minutes ( $\pm$  5 minutes) post completion of infusion
- 13) Blood collection immediately after ( $\pm$  5 minutes) completion of infusion with MEDI-575
  - Serum concentration of MEDI-575
  - Circulating plasma biomarker analysis

**Cycle 2 and All Subsequent Cycles, Study Day 8 (Cohorts 1 through 5 and Weekly Dose-Expansion)**

- 1) Update concomitant medications
- 2) Blood collection prior to infusion of MEDI-575
  - Chemistry panel (AST/ALT, total bilirubin, creatinine, alkaline phosphatase, sodium, potassium, chloride, phosphorus, calcium, glucose, magnesium, albumin, and LDH)
  - Hematology (CBC, differential, and platelet count)
  - Serum concentration of MEDI-575
  - Circulating plasma biomarker analysis
- 3) Routine urinalysis
- 4) Vital signs prior to infusion of MEDI-575 (temperature, blood pressure, pulse rate, respiratory rate)
- 5) Administration of MEDI-575
- 6) Assessment of AEs and SAEs
- 7) Monitor vital signs at 15, 30, and 45 minutes ( $\pm$  5 minutes) post initiation of infusion, at the completion of infusion ( $\pm$  5 minutes), and 30 and 60 minutes ( $\pm$  5 minutes) post completion of infusion
- 8) Blood collection immediately after ( $\pm$  5 minutes) completion of infusion with MEDI-575
  - Serum concentration of MEDI-575
  - Circulating plasma biomarker analysis

**Cycle 2 and All Subsequent Cycles, Study Day 15 (Cohorts 1 through 5 and Weekly Dose-Expansion)**

- 1) Update concomitant medications
- 2) Blood collection prior to infusion of MEDI-575

- Chemistry panel (AST/ALT, total bilirubin, creatinine, alkaline phosphatase, sodium, potassium, chloride, phosphorus, calcium, glucose, magnesium, albumin, and LDH)
  - Hematology (CBC, differential, and platelet count)
  - Serum concentration of MEDI-575
  - Circulating plasma biomarker analysis
- 3) Routine urinalysis
  - 4) Vital signs prior to infusion of MEDI-575 (temperature, blood pressure, pulse rate, respiratory rate)
  - 5) Administration of MEDI-575
  - 6) Assessment of AEs and SAEs
  - 7) Monitor vital signs at 15, 30, and 45 minutes ( $\pm$  5 minutes) post initiation of infusion, at the completion of infusion ( $\pm$  5 minutes), and 30 and 60 minutes ( $\pm$  5 minutes) post completion of infusion
  - 8) Blood collection immediately after ( $\pm$  5 minutes) completion of infusion of MEDI-575
    - Serum concentration of MEDI-575
    - Circulating plasma biomarker analysis

**Every 2 Cycles (Within 3 Days Prior to Subsequent Cycle, Beginning With Cycle 3; All Dose Cohorts and Dose-Expansion Phase)**

*The following evaluations will be performed every 2 cycles (ie, every 6 weeks) unless otherwise indicated, beginning at Cycle 3 (eg, Cycle 3, Cycle 5, etc)*

- 1) Complete physical examination
- 2) Update concomitant medications
- 3) Assess for AEs and SAEs
- 4) Evaluation of disease
  - CT or MRI scans
  - Focused physical examination

**End of Treatment (All Dose Cohorts and Dose-Expansion Phase)**

*The following evaluations will be performed at the time the subject completes therapy or is withdrawn /discontinued from the study therapy, or at the time of the first objective disease*

*progression, whichever comes first. These procedures do not need to be repeated if completed within 14 days of discontinuation of participation.*

- 1) Complete physical examination
- 2) Obtain body weight
- 3) Update concomitant medications
- 4) Assess for AEs and SAEs
- 5) Vital signs (temperature, respiration rate, pulse, blood pressure)
- 6) Evaluation of disease
  - CT or MRI scans
  - Focused physical examination
  - Karnofsky performance status
- 7) Blood collection
  - Chemistry panel (AST/ALT, total bilirubin, creatinine, alkaline phosphatase, sodium, potassium, chloride, phosphorus, calcium, glucose, magnesium, albumin, and LDH)
  - Hematology (CBC, differential, and platelet count)
  - Serum concentration of MEDI-575
  - Circulating plasma biomarker analysis
  - Circulating tumor cell analysis (for Cohorts 6 and 7 and all of the dose-expansion phase)
  - RNA analysis
  - Anti-MEDI-575 antibodies
- 8) Routine urinalysis
- 9) 12-lead ECG. All ECGs performed will be obtained in triplicate (ie, 3 ECGs should be obtained within approximately a 5-minute time interval).

### **30 Days Post Therapy (+ 3 Days; All Dose Cohorts and Dose-Expansion Phase)**

*The following evaluations will be performed at 30 days (+ 3 days) after the last dose of MEDI-575:*

- 1) Complete physical examination
- 2) Obtain body weight
- 3) Update concomitant medications

- 4) Assess for AEs and SAEs
- 5) Assess for subsequent anticancer therapy
- 6) Vital signs (temperature, respiration rate, pulse, blood pressure)
- 7) Evaluation of disease
  - Karnofsky performance status
- 8) Blood collection
  - Chemistry panel (AST/ALT, total bilirubin, creatinine, alkaline phosphatase, sodium, potassium, chloride, phosphorus, calcium, glucose, magnesium, albumin, and LDH)
  - Hematology (CBC, differential, and platelet count)
  - Serum concentration of MEDI-575
  - Anti-MEDI-575 antibodies
  - Circulating plasma biomarker analysis
- 9) Routine urinalysis
- 10) Urine  $\beta$ hCG (women of child bearing potential only)
- 11) 12-lead ECG. All ECGs performed will be obtained in triplicate (ie, 3 ECGs should be obtained within approximately a 5-minute time interval).

**Every 3 Months Post Therapy ( $\pm$  2 Weeks; All Dose Cohorts and Dose Expansion Phase)**

*The following evaluations will be performed every 3 months ( $\pm$ 2 weeks) after the last dose of MEDI-575 as specified:*

- 1) Evaluation of disease (subjects who discontinue treatment due to reasons other than disease progression or initiation of alternative anticancer therapy; these evaluations will be performed until documentation of disease progression, initiation of alternative anticancer therapy, or the end of study [defined as 1 year post entrance of the last subject into the study])
  - CT or MRI scans
  - Focused physical examination
  - Karnofsky performance status
- 2) Blood collection (all subjects)
  - Anti-MEDI-575 antibodies (3 months post last dose, only)
- 3) Survival status and subsequent anticancer therapy by clinic visit or telephone contact until death or the end of the study (all subjects).

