Two additional cohorts will be added to the dose-escalation phase to evaluate 25 mg/kg (Dose Cohort 6) and 35 mg/kg (Dose Cohort 7) administered as a 90-minute IV infusion once every 21 days on Study Day 1 of each cycle. The infusion time is increased for the 25 or 35 mg/kg doses (every 3-week schedule) due to the larger protein load. These subjects will be evaluated identically to other subjects during dose escalation, since the cycle length and DLT period will be 21 days. Subjects in Cohorts 6 and 7 will be considered evaluable if they receive a single dose of MEDI-575 and complete the 21-day DLT period or discontinue due to DLTs. The doses and schedule were chosen based on PK and pharmacodynamic modeling and data obtained in the first 3 treated cohorts, and are predicted to provide target saturation of PDGFR $\alpha$  receptors for the duration of the dosing interval. A minimum of 21 evaluable subjects or up to approximately 42 evaluable subjects will be required during the dose-escalation phase.

Pharmacokinetic/pharmacodynamic modeling was performed based on data generated in cynomolgus monkey PK studies and the first 2 cohorts (3 and 6 mg/kg) from this protocol. The PK/pharmacodynamic model accurately predicted the serum concentrations obtained in humans following the 3, 6, and 9 mg/kg dose of MEDI-575 in this study. Based on the PK/pharmacodynamic modeling, preclinical xenograft efficacy data, and the human data obtained to date, including the measurement of PDGF-AA in the serum, a predicted target average concentration of 250  $\mu$ g/mL and trough levels above 150  $\mu$ g/mL were identified. These concentrations ensure consistent saturation of PDGFR $\alpha$  receptor over the entire dosing interval and are predicted to provide maximum antitumor activity based on animal models. This effect is predicted to be achieved with a dosing schedule of 25 mg/kg or greater administered every 3 weeks. In the current study, no DLTs have been observed in the first 5 cohorts. The increase in dosing interval is under investigation in order to evaluate the feasibility of administration in conjunction with standard chemotherapeutic regimens. This dose regimen will be compared to the once-weekly dosing regimen in the dose-expansion

phase. The prolonged schedule should still allow for adequate blood concentrations as described above to achieve potential antitumor effects.

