**Table 3.6-1 Schedule of Evaluations (Cohorts 1-5 and Dose-Expansion Weekly Schedule): Screening and Treatment Periods**

Evaluations	Screening a	Cycle 1					Cycle 2 and Every Cycle Thereafter			Every 2 Cycles, Beginning With Cycle 3	End of Treatment
		Days 1, 8	Days 2, 9	Days 3, 10	Day 15	Day 22	Day 1	Day 8	Day 15		
Cohort 1											
Cohorts 2 through 5 and dose-expansion weekly schedule		Day 1	Day 2	Day 3	Day 8	Day 15					
Archived Tumor Sample (Optional)	X p										

a To occur within 28 days prior to the first dose of MEDI-575.

b Study Day 1 only.

c Complete physical examination at screening, after every 2 cycles, and at the end of treatment; a focused examination at the start of each cycle.

d These procedures do not need to be repeated if they have been performed within 14 days of disease progression or treatment discontinuation.

e Monitor vital signs prior to infusion, at 15, 30, and 60 minutes (±5 minutes) post initiation of infusion, at the completion of infusion (±5 minutes), and 30 and 60 minutes (±5 minutes) post completion of infusion.

f ECG equipment (with instant print-out and electronic transmission capabilities) and training will be provided to all study sites. All ECGs performed during the study will be obtained in triplicate, ie, 3 ECGs are to be obtained within a 5-minute time interval.

g Prior to infusion, at the time of completion of infusion (± 5 minutes), 2 hours post completion of infusion (± 15 minutes), and 6 hours (± 15 minutes) post completion of infusion. All ECGs should be done prior to PK draw for corresponding time points.

h Prior to the initiation of infusion.

i Prior to infusion on day indicated.

j Includes AST/ALT, total bilirubin, creatinine (and creatinine clearance at screening), alkaline phosphatase, sodium, potassium, chloride, phosphorus, calcium, glucose, magnesium, albumin, and LDH.

k Only those AEs assessed by the investigator as protocol/procedure related. All SAEs are to be reported.

l Prior to infusion, immediately post completion of infusion (± 5 minutes), and 2 hours (± 15 minutes) and 6 hours (± 15 minutes) post completion of infusion.

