**Table 3.6-3 Schedule of Evaluations: Follow-up Period**

All Cohorts and Dose Expansion	Follow-up/Post-therapy	
	30 Days	Every 3 Months
Physical Examination	X	
Weight	X	
12-lead ECG	X	
Vital Signs	X	
Hematology	X	
Serum Chemistry	X	
Routine Urinalysis	X	
Urine $\beta$ hCG	X	
AE/SAE Assessment	X	
Concomitant Medications	X	
CT or MRI Scans		X a
Focused Physical Examination		X a
Karnofsky Performance Status	X	X a
Subsequent Anticancer Therapy	X	X
Survival Status		X
MEDI-575 Serum Concentration	X	
Anti-MEDI-575 Antibodies	X	X b
Circulating Plasma Biomarker Analysis	X	

a For subjects who discontinue treatment due to reasons other than disease progression or initiation of alternative anticancer therapy, disease evaluations will be performed every 3 months until documentation of disease progression, initiation of alternative anticancer therapy, or the end of study (defined as 1 year after the last subject enters the study).

b This test will be performed at 3 months post dose only.

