### **5.5.2 Immunogenicity of MEDI-575**

Immunogenicity of MEDI-575 will be assessed and summarized descriptively by dose cohort.

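### The only antibody sample after the 30-day visit, at 3 months, is also the only antibody draw without a MEDI-575 concentration from the same visit

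*Protocol*

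**What the plan says.** Immunogenicity is the second of the secondary objectives (Section 2.2), and the analysis in Section 5.5.2 reads: "Immunogenicity of MEDI-575 will be assessed and summarized descriptively by dose cohort".

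Antibody samples are scheduled as follows.

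- **Day 1 of every cycle.** Tables 3.6-1 and 3.6-2 place the draw before dosing ("Prior to the initiation of infusion"). Cycle 1 Day 1 is the pre-treatment baseline. A pre-infusion drug concentration is drawn at the same visits.
- **End of treatment.** The blood list in Section 3.6 contains both "Anti-MEDI-575 antibodies" and the drug concentration.
- **30 days after the last dose.** The blood list again contains antibodies and "Serum concentration of MEDI-575".
- **3 months after the last dose (±2 weeks).** The blood list contains one item, "Anti-MEDI-575 antibodies (3 months post last dose, only". Table 3.6-3 agrees: its antibody footnote says "This test will be performed at 3 months post dose only", and its row "MEDI-575 Serum Concentration" is marked at 30 days and left empty at 3 months.

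On drug levels, Section 2.4 gives a target average of 250 µg/mL and "trough levels above 150" µg/mL, predicted for 25 mg/kg or more every 3 weeks. The protocol gives no numerical human half-life, no concentrations for the weekly cohorts, and no assay drug tolerance.

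**The concern.** MEDI-575 is itself an antibody present at high concentration, and free drug in a serum sample can bind anti-drug antibody and keep the assay from detecting it. A negative result is informative only if the drug in that sample is below the level the assay tolerates. The samples up to day 30 are taken on treatment or soon after it. The 3-month sample is the one planned after substantial washout, and so the one most likely to give a readable negative. It is also the one for which nobody will know how much drug was left.

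The summary is by dose cohort. Residual drug is expected to differ by dose, so any masking at this visit could differ along the same axis. Without a measured concentration, that could be neither shown nor ruled out afterwards.

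**Working it through.** **1. Which antibody samples are paired.** A subject who completes c cycles has c − 1 post-baseline Day 1 samples, plus end of treatment, 30 days and 3 months: c + 2 in all. All but the 3-month sample have a concentration from the same visit.

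| Cycles | Post-baseline antibody samples | Paired with a concentration |
|---|---|---|
| 1 | 3 | 2 |
| 2 | 4 | 3 |
| 4 | 6 | 5 |
| 8 | 10 | 9 |

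The visit list and Table 3.6-3 agree, so this is the schedule as intended and not a slip in one place.

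**2. Half-life implied by the protocol's targets.** There is no plan figure to reproduce, so this step is illustrative. Inputs from Section 2.4: average 250 µg/mL, trough 150 µg/mL, dosing interval 21 days, taken as the levels for 25 mg/kg. Assumptions: one compartment, linear clearance, bolus input, steady state. With x = k × 21,

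trough / average = x / (eˣ − 1) = 150 / 250 = 0.60

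which gives x = 0.947, k = 0.947 / 21 = 0.0451 per day, half-life = 0.693 / 0.0451 = 15.4 days, and peak = 150 × e^0.947 ≈ 387 µg/mL.

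**3. Residual drug after the last 25 mg/kg dose.** C(t) = 387 × e^(−0.0451 t). The 3-month visit is taken as day 90, with a window of days 76 to 104.

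| Day after last dose | µg/mL |
|---|---|
| 30 | about 100 |
| 76 | 12.6 |
| 90 | 6.7 |
| 104 | 3.6 |

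The visit window alone changes the level by a factor of 12.6 / 3.6 = 3.5.

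**4. Sensitivity to half-life.** Holding the trough at 150 µg/mL on day 21 and varying the half-life as an assumption, C(90) = 150 × 2^(−69 / half-life).

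| Half-life (days) | Day 90 (µg/mL) |
|---|---|
| 7 | 0.16 |
| 14 | 4.9 |
| 21 | 15 |
| 28 | 27 |

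The calendar date therefore does not tell the analyst whether drug is nearly gone or still in the tens of µg/mL.

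**5. Does this become a difference between dose cohorts?** Under the same linear model, day-90 levels are 1.8, 3.6, 5.4, 7.2 and 9.1 µg/mL for the weekly cohorts at 3, 6, 9, 12 and 15 mg/kg, and 6.7 and 9.3 µg/mL for 25 and 35 mg/kg every 3 weeks. For a 3-month sample on day 90:

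- an assumed tolerance of 1 µg/mL leaves no cohort readable;
- 10 µg/mL leaves every cohort readable;
- 5 µg/mL splits them, with only 3 and 6 mg/kg readable.

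The split also moves with the visit date. By day 104 every cohort is below 5 µg/mL (highest 4.97), while on day 76 all cohorts from 9 mg/kg upward exceed 10 µg/mL.

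**The case against.** The strongest reply is that most samples are already paired. Negatives on Day 1 of each cycle, at end of treatment and at 30 days can be classed as conclusive or inconclusive once the assay's tolerance is known. This stands. A reader might infer from the high target troughs that no negative result in the trial can be interpreted, but the documents do not support that: the gap is confined to the 3-month sample.

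A reader might also infer that measured immunogenicity will fall with dose. The documents do not support that either. It depends on an unstated assay tolerance, and at two of the three tolerances tried in the working, no contrast between cohorts arises on day 90. Differential masking is a possibility, not a result.

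Third, the 3-month sample is not worthless without a concentration. A positive remains informative, and residual drug could be extrapolated from the end-of-treatment and 30-day levels. This stands in part. The extrapolation would reach from day 30 to somewhere between days 76 and 104, that is 46 to 74 days past the last measurement, for a drug whose clearance the protocol describes as dose-dependent in monkeys (Section 1.3). An estimate is possible, but it is a poor substitute for a direct reading.

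Fourth, rules for masked or inconclusive samples belong in the statistical analysis plan. That stands, and their absence from Section 5.5.2 is not held against the protocol. The blood test itself is different: an analysis plan cannot supply a measurement that was never scheduled.

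**Conclusion.** The point holds as a gap in the sampling schedule. The single antibody draw after the 30-day visit has no concentration from the same visit, so a negative there cannot be directly separated from drug interference, and antibody rates by dose cohort may be biased. Whether they are, and by how much, depends on the assay's drug tolerance.

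The size is uncertain: about 4 to 13 µg/mL of residual drug across the visit window for 25 mg/kg every 3 weeks, and about 0.2 to 27 µg/mL at day 90 over the assumed half-lives. These figures rest on linear one-compartment kinetics at steady state and on treating a target trough stated as a lower bound as if it were exact. A higher trough at the same average would imply a longer half-life and more residual drug. Faster clearance at low concentrations, or stopping before steady state, would give less. The levels for the weekly cohorts are linear scalings, not protocol figures.

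The consequence is limited to a descriptive secondary endpoint. Dose-limiting toxicity, dose escalation and sample size are untouched. The change is worth making because it is cheap and cannot be made after the samples are taken.

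**What to change.** Add MEDI-575 serum concentration to the 3-month draw in two places: the 3-month column of Table 3.6-3, with the same footnote restriction as the antibody test, and the blood collection item in the Section 3.6 list for visits every 3 months post therapy. Every antibody result would then have a drug level from the same visit.

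The cost is one extra assay per subject on blood that is already drawn. Some 3-month negatives may then have to be reported as inconclusive. How samples above the assay's tolerance are classified and summarized can be left to the statistical analysis plan.
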